5.1.3. Exploratory Endpoints

Patient-Reported Outcomes Measurement Information System (PROMIS), a state-of-the-science PRO measurement system, was developed using mixed qualitative and quantitative methods and uses item response theory-calibrated item banks for numerous patient-reported symptoms and functional domains. The PROMIS Global Health 10 measure comprises ten items with two summary scores for physical and mental functioning with higher scores indicating better

functioning. Those two summary scores will be calculated using the Assessment Center Scoring Service (https://www.assessmentcenter.net/ac_scoringservice) from raw data.

5.2. Safety Endpoints

5.2.1. Adverse Events

Adverse Event

Adverse event (AE) is defined as any untoward medical occurrence in a patient administered the study medication and which does not necessarily have to have a causal relationship with the treatment.

Treatment Emergent Adverse Event

Treatment emergent adverse events (TEAE) are any AEs occurring or worsening in severity after the first administration of study medication.

Significant Adverse Event

Significant adverse events are any AEs leading to additional pertinent intervention (such as dose interruption, dose reduction or dose discontinuation).

Causality of Adverse Event

The causality with BN101/belumosudil will be classified into following 5 classes: definitely related, possibly related, unlikely related, not related, and not determined. Definitely related, possibly related, and not determined will be considered related in the analysis of related AEs.

Serious Adverse Event (SAE)

Serious adverse events (SAE) are any AE which happens during any study period (screening period, treatment period, follow up period) with any dose of the study medication and which meet one or more following criteria. Treatment emergent SAE will be summarized in the analysis.

- Result in death
- Life threatening
- Requires inpatient hospitalization or prolongation of existing hospitalization
- Result in persistent or significant disability / incapacity
- Result in a congenital anomaly / birth defect
- Other important medical events

Death

All AEs leading to death will be recorded in CRF. Death report will also be collected in CRF.

Severity of Adverse Events

Adverse event will be graded using the National Cancer Institute (NCI) Common Terminology Criteria for Adverse Events (CTCAE) version 5.0:

Grade 1: Mild; asymptomatic or mild symptoms; clinical or diagnostic observations only; intervention not indicated.

Grade 2: Moderate; minimal, local or noninvasive intervention indicated; limiting age-appropriate instrumental Activities of Daily Living (ADL) (instrumental ADL refer to preparing meals, shopping for groceries or clothes, using the telephone, managing money, etc)

Grade 3: Severe or medically significant but not immediately life-threatening; hospitalization or prolongation of hospitalization indicated; disabling; limiting self care ADL (self care ADL refer to bathing, dressing and undressing, feeding self, using the toilet, taking medications, and not bedridden)

Grade 4: Life threatening consequences; urgent intervention indicated.

Grade 5: Death related to AE.

5.2.2. Vital Signs

Body temperature, pulse, blood pressure (systolic pressure and diastolic pressure) and overall assessment will be collected in CRF.

5.2.3. 12 Lead-ECG

12 lead-ECG results (heart rate, RR interval, PR interval, QT interval, QTcB interval, QTcF interval, QRS wave and overall assessment) will be collected in CRF.

5.2.4. Laboratory Evaluations

Hematology, chemistry, and urinalysis will be collected in CRF.

5.2.5. Eastern Cooperative Oncology Group (ECOG) Performance Status (PS) Score

ECOG PS score will be collected in CRF.

5.3. Pharmacokinetic Variables

Pharmacokinetic variables will be presented in a separate PK analysis plan.

5.4. Protocol Deviation

All protocol deviations will be identified and classified as major or minor (as defined below) before the clinical database lock.

Major Deviations: Protocol deviation that may impact the accuracy, and/or reliability of the study data or that may impact patient rights, safety or well-being.

Minor Deviations: Protocol deviation that does not impact the accuracy, and/or reliability of the study data or patient rights, safety or well-being.

5.5. Treatment Compliance and Exposure

The extent of BN101/belumosudil exposure will be assessed using the duration of BN101/belumosudil treatment.

Duration of treatment (days) = last dose date – first dose date + 1 regardless of unplanned intermittent discontinuations.

The cumulative duration of treatment will be provided, defined as the sum of the duration of treatment for all patients, and will be expressed in patient years.

The relative dose intensity (RDI) will be presented. The RDI is defined as:

$$\text{RDI (\%)} = 100\% * \text{ADI (mg/day)} / \text{PDI (mg/day)} .$$

Where ADI and PDI are the actual dose intensity and planned dose intensity, respectively::

$$\text{ADI (mg/day)} = \text{actual cumulative dose (mg)} / \text{duration of treatment (days)}$$

$$\text{PDI (mg/day)} = \text{planned cumulative dose (mg)} / \text{duration of treatment (days)}$$

The planned cumulative dose is the planned daily dose * duration of treatment, while the actual cumulative dose is the sum of actual doses received over the duration of treatment. The actual total dose will incorporate information of dose reduction and dose interruptions captured in the CRF.

6. Statistical Hypothesis

Since this study intend to evaluate the consistency of the efficacy, safety and PK profile of belumosudil between Chinese cGVHD patients and Caucasian cGVHD patients for the purpose of bridging the results of KD025-213 study, no formal hypothesis testing will be performed. All statistical analyses will be descriptive.

7. Analysis Population

Modified Intent-to-treat (mITT)

mITT: The primary population for efficacy analyses will be a modified Intent to treat (mITT) population defined as all enrolled patients who receive at least one dose of study medication.

The mITT population will be used for tables of demography, baseline characteristics and efficacy.

Responder: The responder population is defined as patients in the mITT population that achieved a partial or complete response at any post-baseline response assessment.

Nonresponder: The nonresponder population is defined as anyone in mITT population that is not a responder.

The responder and nonresponder populations will be used for some subgroup analyses.

Safety Set (SS)

The safety population is defined as all enrolled patients who receive at least one dose of study medication and have at least one post-baseline safety assessment. Safety population will be used for all safety analyses.

Per-protocol Set (PPS)

The per-protocol population is defined as a subset of mITT, including all enrolled patients who receive at least one dose of study medication without major protocol deviations. PPS will be used for sensitivity analyses of primary efficacy analysis.

8. Statistical Methods

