1.6 Rationale for the design of this study

As BN101/belumosudil has completed clinical development for cGVHD in the U.S., the registration study (KD025-213) met clinical endpoints and supported the conclusion that benefits outweighed risks. A rolling submission NDA for the cGVHD indication based on this study was also completed at the end of November 2020 and was fully approved by the FDA on July 16, 2021 in the United States. Given the global development status of BN101/belumosudil in the cGVHD indication, and based on the recommendation of the NMPA, we first conducted a PK bridging clinical trial in healthy volunteers to initially assess the safety, drug exposure and metabolites of BN101/belumosudil in healthy individuals to determine the BN101/ belumosudil starting dose and PK profile. Given that the PK bridging clinical trial in healthy volunteers has been substantially completed and met the bridging objective, the Sponsor currently plans to conduct a bridging study to evaluate the efficacy, safety and PK characteristics of BN101/belumosudil for the treatment of Chinese patients with cGVHD. This bridging study is an open, single-arm trial in Chinese patients with cGVHD, and because it is designed for bridging purposes, the sample size is not determined by statistical assumptions.

This study is planned to enroll 30 patients with cGVHD who have undergone at least 1 but not more than 5 lines of systemic therapy. Considering that the recommended dose of both cGVHD clinical trials in Western populations was 200 mg QD and the highest administered dose of BN101/belumosudil in the phase I dose-escalation study reached 1000 mg QD/500 mg BID and

was well tolerated, combined with the pharmacokinetic profile of 200 mg orally in the phase I study in Chinese healthy volunteers was consistent with the results in the overseas study, without any TEAE associated with the investigational drug, the starting dose of this cGVHD bridging clinical trial was also set at 200 mg QD.

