The study enrollment period is estimated to be 6 months. 6 months after the last patient enrollment, the database will be locked and the primary analysis will be conducted. After primary analysis, all patients will be followed up for additional 6 months and a follow up analysis will be conducted 12 months after the last patient enrollment.

Eligible patients who have signed informed consent will be enrolled to receive BN101/belumosudil (every 28-day cycle) until cGVHD progression, intolerable toxicity, initiation of a new cGVHD therapy, recurrence of hematological neoplasm, loss to follow-up,

withdrawal of consent, or death, whichever occurs first. During study, concomitant treatment with standard of care systemic cGVHD therapies such as corticosteroids, calcineurin inhibitors (tacrolimus, cyclosporine), sirolimus, MMF, or extracorporeal photopheresis (ECP), are permitted as long as the patient has been on a stable dose / regimen of these per the eligibility criteria. Initiation of new systemic cGVHD therapy while on study is not permitted. Response criteria will be assessed after cycles 1, 2, 3 and 4 and then after every other cycle thereafter (i.e. on Day 1 of Cycle 2, 3, 4, 5, 7, 9, 11 etc). For patients assessed as "Lack of Response - Mixed" and "Lack of Response - Progression" [Evaluated by the investigator based on the National Institutes of Health (NIH) Consensus Development Project on Criteria for Clinical Trials in cGVHD(2014), hereinafter referred to as the NIH Consensus Criteria (2014)], if the investigator believed that these patients could continue to benefit from treatment with BN101/belumosudil, the treatment may be continued after a written application was submitted, and approval from the Sponsor's Medical Monitor as well as documentation of the patient's willingness to continue treatment was obtained. For patients who did not achieve any response after 12 cycles of BN101/belumosudil treatment, they should discontinue the study medication and withdraw from the study if in the investigator's judgment there is no evidence of clinical benefit (e.g., improvements in organ score, improvements in Lee symptom scores, reductions of corticosteroid/tacrolimus doses). For patients whose cGVHD has not progressed at the time of discontinuation of the study treatment and who come off study for reasons other than AEs should be tapered off BN101/belumosudil by reducing the dose every other week (200mg QD → 200mg QOD → discontinue).

5. Study Endpoints

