8.3.8. Treatment Compliance and Exposure

Treatment compliance and exposure will be analyzed on mITT population.

Duration of treatment and duration of follow up will be summarized as a continuous variable and also categorically by numbers and percentages for each category (0-3 months, 3-6 months, 6-9 months, >9 months).

Descriptive summary statistics of cumulative exposure (patient year), actual cumulative dose (mg), ADI (mg/day), RDI (%) and RDI as a categorical endpoint (>95%, ≤95%) will be presented.

Number and percentage of patients for each RDI category (<80%, 80-100%, >100%) will be summarized by visit.

Number and percentage of patients with dose reduction and dose interruption will be summarized.

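### The SAP's relative dose intensity makes no provision for the planned QOD taper, so a patient who takes every instructed dose can score below 100% (minor, descriptive)

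*SAP*

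**What the plan says.** SAP 5.5 defines RDI as actual over planned dose intensity. Both intensities are divided by the same duration of treatment, so RDI reduces to actual cumulative dose over planned cumulative dose.

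- **Denominator:** "The planned cumulative dose is the planned daily dose * duration of treatment".
- **Duration:** counted inclusively up to the last dose, measured from "first dose date + 1 regardless of unplanned intermittent discontinuations".
- **Numerator:** the doses actually received; "The actual total dose will incorporate information of dose reduction and dose interruptions captured in the CRF".
- **Planned daily dose:** not defined in the SAP. Protocol 1.6 says "the starting dose of this cGVHD bridging clinical trial was also set at 200 mg QD".
- **Taper:** SAP 4 applies it to patients whose cGVHD has not progressed and "who come off study for reasons other than AEs should be tapered off BN101/belumosudil by reducing the dose every other week", from 200 mg daily to 200 mg on alternate days and then to stopping. Protocol 3.5 and 4.1 describe the same sequence in two-week steps. Their two conditions (no progression; a non-AE reason for leaving) are joined by 'or', where the SAP joins them by 'and'.
- **Reporting:** SAP 8.3.8 splits overall RDI at 95% and bands RDI by visit (<80%, 80–100%, >100%). It adds: "Number and percentage of patients with dose reduction and dose interruption will be summarized".

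Neither SAP 5.5 nor SAP 8.3.8 mentions the taper.

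**The concern.** During the taper a compliant patient takes a tablet on alternate days. If the denominator still accrues 200 mg for every calendar day, those days are scored as half-dosed although nothing was missed. The error runs in one direction, towards apparent under-dosing, and is largest in patients treated for a short time.

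The SAP sections concerned cover compliance as well as exposure, but RDI is the only adherence-type measure they contain. Protocol 6.5 defines a compliance ratio of amount taken to amount due, under which the same patient would score 100%. The SAP does not carry that ratio over.

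SAP 4 itself describes the taper as reducing the dose. A programmer could therefore reasonably include it in the SAP 8.3.8 dose-reduction count, which would mix scheduled tapering with other reductions.

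**Working it through.** The documents state no RDI value, so there is no figure to reproduce. The SAP formula is applied to a patient who takes every instructed dose.

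**Inputs**
- Planned daily dose: constant 200 mg (assumption; Protocol 1.6 gives the starting dose).
- D: number of days on 200 mg QD before the taper.
- Taper: one 14-day QOD step with 7 doses (Protocol 3.5 and 4.1, two-week steps).
- Cut-offs: 95% overall and 80% by visit (SAP 8.3.8).

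**Formula.** Doses taken are D + 7. The span from first to last dose depends on when alternate-day dosing begins:
- (a) first QOD dose on the day after the last QD dose: span D + 13, so RDI = (D + 7)/(D + 13);
- (b) first QOD dose two days after: span D + 14, so RDI = (D + 7)/(D + 14).

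The 200 mg cancels.

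| D (QD days) | (b) | (a) |
|---|---|---|
| 28 | 35/42 = 83.3% | 35/41 = 85.4% |
| 56 | 63/70 = 90.0% | 63/69 = 91.3% |
| 84 | 91/98 = 92.9% | 91/97 = 93.8% |
| 112 | 119/126 = 94.4% | 119/125 = 95.2% |
| 168 | 175/182 = 96.2% | 175/181 = 96.7% |
| 336 | 343/350 = 98.0% | 343/349 = 98.3% |

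**Overall 95% cut-off**
- (a) D + 7 ≤ 0.95(D + 13) gives 0.05D ≤ 5.35, so D ≤ 107.
- (b) D + 7 ≤ 0.95(D + 14) gives 0.05D ≤ 6.3, so D ≤ 126.

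That is about 3.8 to 4.5 cycles of 28 days. A compliant patient tapered later stays above 95%.

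**By-visit bands**
- 28-day interval with 14 QD days plus the taper: 21/28 = 75.0% or 21/27 = 77.8%, both below 80%.
- 56-day interval with 42 QD days plus the taper: 49/56 = 87.5% or 49/55 = 89.1%, both above 80%.

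The by-visit result depends on how the last interval is cut, which the SAP does not say. It does not depend on how long earlier treatment lasted.

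**After the fix.** With the taper planned at its own schedule, the numerator and denominator are both 200 × (D + 7) mg, so RDI is 100% for every D and every interval.

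**The case against.** The strongest objection is that the planned daily dose is simply undefined. If it were programmed by treatment phase, averaging 100 mg/day during QOD dosing, the problem would vanish. That stands as a limit on certainty. It does not remove the point, because the SAP's wording has one daily dose multiplied by the whole period and nothing directs the programmer otherwise.

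Second, the taper occasions that the documents identify come mostly late. The rule for stopping without response or benefit applies after 12 cycles (12 × 28 = 336 days, RDI about 98%), and the main study ends 12 months after the last enrolment. Under the SAP's 'and', patients who stop for progression or an AE are not tapered. This stands for the SAP wording. Under the protocol's 'or', read literally, a patient leaving for progression could also be tapered. Response visits after 28, 56, 84 and 112 days fall in the range where the 95% split can be affected.

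Third, tolerability is reported elsewhere. Protocol 8.6.1.7 ties the AE action of dose reduction to a specific AE, and SAP 8.5.1 tabulates TEAEs leading to dose reduction separately. Those tables are safe. Only the unlabelled count in SAP 8.3.8 is open, and counting the taper there is possible, not certain.

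A reader might go further and infer that each tapered patient shifts the percentages by 1/30 = 3.3 points. That does not follow: a patient tapered after day 107 or 126 does not cross the 95% split, and by-visit denominators need not be 30. A reader might also infer a bias relative to KD025-213. The documents do not show how that study computed RDI or handled a taper, so no such bias can be claimed.

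**Conclusion.** The point holds as a minor correction to a descriptive table. On the plain reading of SAP 5.5, with a constant 200 mg planned daily dose and a 14-day, 7-dose QOD step, a fully compliant tapered patient scores below 100%. The shortfall is roughly 15 to 17 points after one cycle and 2 to 4 points after 6 to 12 cycles. Misclassification into the ≤95% group is confined to patients tapered within about 107 to 126 QD days. Entry to the by-visit <80% band is possible at any treatment length but depends on interval binning.

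Patients who stop without a taper, or who are still on drug at data cut-off, are not affected. How many patients will taper cannot be derived from the documents, and the eligibility wording (SAP 'and', protocol 'or') must be reconciled before anyone can say who should. The documents do not support reading this as a threat to ORR, to any other efficacy endpoint or to the AE-based tables. The study tests no hypothesis, and no decision rule uses RDI.

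**What to change.** In SAP 5.5, define the planned cumulative dose as the sum of protocol-scheduled doses, with the planned dose during a protocol taper equal to the taper schedule. Leave duration of treatment and actual cumulative dose as they are. This is preferable to ending the RDI window before the taper, which would create two durations and leave it unclear whether taper doses count in the cumulative dose.

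In SAP 8.3.8, state that a planned taper is excluded from the dose-reduction count and report the number of tapered patients in its own row. Reconcile the taper eligibility wording between SAP 4 and Protocol 3.5 and 4.1; this review takes no position on which wording is right.

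The cost is a few lines of SAP text and a flag on the dosing record that separates a planned taper from other dose changes. If comparison with KD025-213 calls for it, RDI against a constant 200 mg/day can be kept as a supplementary row.

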8.1. General Consideration

In the line listing, subject ID (site ID-patient screening number) will be the only universal identifier for the patient.

General rule for the statistical description: continuous variables will be summarized by descriptive statistics of mean, median, standard deviation, minimum and maximum. Categorical variables will be summarized with counts and corresponding percentages.

All analyses will be conducted using SAS version 9.4 or higher.

Baseline

Baseline is defined as the last non-missing measurement or assessment taken on or prior to first administration of the study medication.

Study Day
Study day will be calculated from the date of first administration of the study medication.
If the date of event / assessment / sample collection is prior to the first administration of the study medication:

Study day = date of event / assessment / sample collection – date of first administration of the study medication

The day before the date of first dose will be study day -1.

If the date of event / assessment / sample collection is after the first administration of the study medication:

Study day = date of event / assessment / sample collection – date of first administration of the study medication +1

The day of the first administration of the study medication is study day 1.

Unless otherwise specified, unscheduled measurements will not be included in the by-visit summaries, but will contribute to best / worst case value, minimum / maximum changes, or abnormal or significant observations where required (e.g. shift table).

8.2. Handling of Data

8.2.1. Incomplete or Missing Data

Unless otherwise specified, the missing data will not be imputed. If the missing data is categorical, it should be classified as “missing” or “unknown”.

Incomplete or Missing Start Date and End Date of AE, Prior / Concomitant Medication, Prior / Concomitant Non-medication Treatment

Imputation of missing start date and end date of AE, prior/concomitant medication, prior/concomitant non-medication treatment is intended to decide the precedence relationship of the event relative to the first administration of the study medication. Unimputed date will be presented in the listing.

- Incomplete or Missing Onset Date

If onset year and month are known and onset year and month are prior to the year and month of first dose of study treatment, the onset date will be imputed as the 1st day of onset month. If onset year and month are equal to the year and month of first dose of study treatment, then the onset date will be imputed as the date of first dose of study treatment.

If only onset year is known, then the onset date will be imputed as January 1st. If onset year is equal to the year of first dose of study treatment, then the onset date will be imputed as the date of first dose of study treatment.

If onset year, month and date are all missing, then the onset date will be imputed as the date of first dose of study treatment.

Note: when the onset date is imputed, it should be on or prior to the end date of event.

- Incomplete or Missing End Date

If end year and month are known, the end date will be imputed with the last day of end month. If the imputed date is later than the latest assessment date, then the end date will be imputed as the latest assessment date.

If end year is known, the end date will be imputed as the December 31st. If the imputed date is later than the latest assessment date, then the end date will be imputed as the latest assessment date.

If end year, month and date are all missing, it should be determined whether the event is ongoing. If the variable of ongoing or not is yes or missing, then the end date will not be imputed. If the variable of ongoing or not is not, then the end date will be imputed as the latest assessment date.

Incomplete or Missing Event Date in Time to Event Analyses

In time to event analyses, if the year and month of event are known, the event date will be imputed conservatively. If the event is not anticipated, then the event date will be imputed as the 1st day of the month. If the event is neutral, then the date will be imputed as the 15th of the month. If the event is anticipated, then the event date will be imputed as the last day of the month.

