5.1.2. Secondary Efficacy Endpoints

Secondary efficacy endpoints include Duration of Response (DoR), Lee Symptom Scale Score (LSS), Response by Organ System, Time to Response, Time to Next Therapy, Corticosteroid Dose, Calcineurin Inhibitor (CNI) Dose, Failure Free Survival (FFS), Overall Survival (OS), Change in cGVHD severity using the Clinician-Reported Global cGVHD Activity Assessment, and Change in symptom activity using the cGVHD Activity Assessment Patient Self-Report.

DoR

Four definitions of DoR are as following:

The primary definition of DoR is the time from first documentation of response to the time of first documentation of deterioration from best response (e.g., CR to PR, or PR to LR).

The secondary definition of DoR is the time from first documentation of response to the time of first documentation of lack of response.

The tertiary definition of DoR is the time from first documentation of response to the time of initiation of new systemic cGVHD therapy.

The quaternary definition of DoR is the time from first documentation of response to the time of first documentation of lack of response (as the secondary definition) but with durations summed for multiple response / lack of response episodes.

The DoR will be reported only for responders. And the censoring rules in [Table 2](#) will be applied.

Lee Symptom Scale Score (LSS)

Lee cGVHD Symptom Scale will be assessed on Day 1 of Cycles 2-5, then on Day 1 of every other Cycle thereafter and EOT. The questionnaire consists 30 items of 7 domains: skin, eyes and mouth, breathing, eating and digestion, muscles and joints, energy, and emotional. Each question is scored 0, 1, 2, 3 or 4.

A domain score will be calculated for each domain by taking the mean of all items completed if more than 50% were answered and normalizing to a 0 to 100 scale. A summary score will be calculated as average of all domain scores if more than 50% of them are nonmissing. A higher score indicated more bothersome symptoms. 7 points difference on the summary score of cGVHD symptom scale was found to be clinically meaningful.

$Raw\ Score = (I_1 + \dots + I_m) / m$, m is the number of items have nonmissing value in a domain.

$$Domain\ Score = Raw\ Score / 4 * 100.$$

$Summary\ Score = (Domain\ Score_1 + \dots + Domain\ Score_n) / n$, n is the number of domains have nonmissing domain scores.

Response by Organ System

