8.4.2. Analyses for Secondary Endpoints

DoR

DoR will be analysed only based on responder population. Kaplan-Meier plots and descriptive statistics of DoR will be provided. The censoring rules in [Table 2](#) will be applied. Landmark analyses with number and percentage of patients with response sustained for ≥ 12 , ≥ 16 , ≥ 20 , ≥ 24 , ≥ 32 , ≥ 40 and ≥ 48 weeks will be provided.

Table 2 Censoring Rules for Duration of Response

| DoR | Events | Censoring |
|------------|--|--|
| Primary | 
 • Deterioration from best response • Initiation of new systemic therapy for cGVHD • Death 
If deterioration from best response or initiation of new systemic therapy happens immediately after two or more missed response assessments, the event date should be set as four weeks (one cycle) after last documented response assessment prior this event.
 | Last documented response assessment |
| Secondary | 
 • Documented LR • Initiation of new systemic therapy for cGVHD • Death 
If LR or initiation of new systemic therapy happens immediately after two or more missed response assessments, the event date should be set as four weeks (one cycle) after last documented response assessment prior this event.
 | |
| Tertiary | 
 • Initiation of new systemic therapy for cGVHD • Death | Last response assessment or long term follow up assessment, whichever is the latest and available. |
| Quaternary | 
 • LR • Initiation of new systemic therapy for cGVHD • Death 
With summation of DoR from multiple episodes.
 | Same with censoring rule for primary and secondary. |

Lee Symptom Scale Score (LSS)

The analyses will be performed based on mITT, responder and nonresponder population. The analyses will include:

- Both scores and change from baseline values (summary score and domain scores) will be summarized as continuous variables by visit.
- Number and percent of patients with a ≥ 7 point reduction (7-PtR) from baseline.

- Number and percent of patients with a 7-PtR from baseline on 2 consecutive assessments.
- Duration of a 7-PtR (DO7-PtR) (defined as time from documentation of the first \geq 7-point resolution to the first documentation of less than 7-point reduction). If there are multiple episodes, the DO7-PtR will be measured as the sum of DO7-PtR from all episodes.

Response by Organ System

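### Partial dates in the time-to-event analyses have no lower bound, so an imputed failure can precede a contact that found the patient event-free

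*SAP*

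**What the plan says.** SAP 8.2.1 has a short rule for time-to-event analyses when year and month are known. It says the imputation is meant to be conservative and gives three cases. The first reads: "If the event is not anticipated, then the event date will be imputed as the 1st day of the month". Of the other two, neutral events go to the 15th and anticipated ones to month end. No endpoint event is assigned to a class, and no bound is given at first dose, first response, last assessment or data cut-off.

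The same section treats adverse events and prior or concomitant treatments differently. If onset falls in the month of first dose, "then the onset date will be imputed as the date of first dose of study treatment". If an imputed end date runs past the latest assessment, "then the end date will be imputed as the latest assessment date". There is also a ceiling on onset: "Note: when the onset date is imputed, it should be on or prior to the end date of event". The stated purpose of these rules is to place the record relative to first dose, and they are not extended to endpoint events.

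The only other rule that moves an event date is in Table 2 (SAP 8.4.2). For deterioration, lack of response or new therapy straight after two or more missed assessments, "the event date should be set as four weeks (one cycle) after last documented response assessment prior this event". It appears only under the primary and secondary definitions of DoR. Tertiary DoR, which is "the time from first documentation of response to the time of initiation of new systemic cGVHD therapy", has no such rule, and neither do TTNT, FFS and OS.

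**The concern.** A month-only date says that the event happened somewhere in that month. Other records often narrow the window: a clinic visit or telephone call in the same month at which the patient was alive, relapse-free and on no new therapy. The SAP rule ignores that information. Where the 1st precedes such a contact, the analysis dataset places a failure before a record that shows no failure had occurred. If the event shares a month with first response or first dose, the duration can be negative, and the SAP does not say how a negative time enters a Kaplan-Meier analysis.

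Partial dates are plausible for these events. After study drug stops, survival, changes in cGVHD therapy and antitumour therapy are learned by telephone about every 12 weeks (Protocol 4.3.6), and these map closely onto the components of FFS. With 30 patients, a single misdated event is visible in a curve or a landmark count.

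**Working it through.** **Inputs.** Imputation rule: SAP 8.2.1. Response assessments: Day 1 of Cycles 2 to 5 in 28-day cycles, then every second cycle, so 28 and then 56 days apart (SAP 4). Telephone follow-up: about 12 weeks, or 84 days (Protocol 4.3.6). DoR starts at first response; OS and TTNT start at first dose or treatment (SAP 5.1.2). No sample size, power or alpha figure depends on the rule, so the plan has no figure of its own to reproduce. Durations below are simple date differences. The dates are constructed, and all events are treated as not anticipated.

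**Failure dated before an event-free visit.** First dose 20 January 2022; visits on 17 February (C2D1), 17 March, 14 April and 12 May (C5D1). Response is first seen on 17 February and still present on 12 May. New therapy is recorded as May, day missing.
- Rule date: 1 May. DoR = 11 + 31 + 30 + 1 = 73 days = 10.4 weeks.
- Documented response: 17 February to 12 May = 84 days = 12.0 weeks.
- With a floor at the day after the last event-free contact: 13 May, so DoR = 85 days.

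The patient fails the 12-week landmark in SAP 8.4.2 although a visit documents response at 12 weeks. No assessment was missed, so the Table 2 substitution does not apply.

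**Negative duration.** Same patient, but new therapy is recorded as February. Rule date 1 February; DoR = 1 − 17 = −16 days. With the floor: 18 February, DoR = +1 day.

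**Before first dose.** First dose 10 March, seen alive 18 March, death recorded as March. Rule date 1 March, 9 days before first dose. With the floor: 19 March, 9 days after it.

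**How often.** Assume the true event day is uniform over 2022–2023 and the gap g since the last event-free contact is uniform on 1 to G days. Let s be day of month minus 1; its mean is 14.72 and its maximum is 30. The rule date is strictly before the contact when g < s. Ignoring a small truncation at G = 28, the proportion is mean(max(s − 1, 0)) / G. That mean is 14.72 − 1 + 24/730 = 13.75, where 24/730 allows for the days that are already the 1st.
- G = 84: 13.75/84 = 16.4%
- G = 56: 13.75/56 = 24.6%
- G = 28: 13.75/28 = 49.1%

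Full enumeration gives the same three figures. A floor at the day after the contact also moves ties, so the share of dates it changes is slightly larger: 17.5%, 26.3% and 52.3% by enumeration. Under the 15th-of-month rule the strictly-before shares are 4.4%, 6.5% and 13.1%.

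**Two rules for one record.** A new cGVHD therapy entered as a concomitant treatment in the first-dose month gets the first-dose date under the medication rule and the 1st under the time-to-event rule. The SAP does not say which prevails.

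**The case against.** The strongest reply is that the rule is openly conservative, the endpoints are secondary and descriptive, no hypothesis is tested (SAP 6), and the awkward cases are rare. New systemic therapy is prohibited on treatment (Protocol 6.4.8), and cGVHD therapies are recorded until 28 days after the last dose (Protocol Appendix 1). Deaths in that period are reported within 24 hours (Protocol 8.7.2), and a fatal adverse event needs a recorded time of death (Protocol 8.6.1.8). Events before first response or first dose need several coincidences. Much of this stands: it limits the frequency and makes this a minor point. It does not justify a date that recorded data rule out. The floored date is still the earliest possible one, so the conservative intent survives. Outlier queries (SAP 8.2.2) do not solve it either, since a query cannot recover a day nobody knows and a DoR of 73 days does not look odd.

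Three stronger readings are tempting, and the documents do not support them.
- A reader might infer that the SAP always sends death, new therapy and loss of response to the 1st. It assigns no event to a class; placing new therapy, relapse and death there is only the natural reading of its conservative intent. Loss of response is found at assessments and carries a visit date.
- A reader might size the defect by the average backward shift: 14.7 days, or 14.7/147.7 = 10% of the 21.1-week median DoR quoted from KD025-213 (Protocol 1.4.2). That measures the disclosed choice of the 1st, most of which would remain after a floor is added under 84-day contacts. It is not the effect of the missing bound.
- A reader might infer that ORR is affected. SAP 5.1.1 disregards responses on or after new systemic therapy, so an early imputed start could remove a response, but only if that date is reused there. The SAP states the rule for time-to-event analyses alone.

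Table 2 also deserves credit: its substitute date cannot precede the last assessment. It partly covers primary and secondary DoR, although the SAP does not say whether assessments after discontinuation count as missed.

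**Conclusion.** The point holds as a minor, easily corrected defect. Followed as written, the rule can give dates that contradict recorded data and possibly negative durations. The exposure is mainly new therapy, relapse and death in tertiary DoR, TTNT, FFS and OS. The documents do not say how many dates will be partial, so the total effect cannot be sized. Per partial date set to the 1st, the chance of falling before the last event-free contact is about 16% with telephone contacts, the setting where partial dates are most likely, rising to 25% and 49% at the clinic-visit intervals. These shares rest on uniform event timing and on the events being classed as not anticipated. Early dating usually shortens durations, so the problem is impossible date order and not a bias in favour of the drug.

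**What to change.** Amend the time-to-event paragraph of SAP 8.2.1 before database lock:

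1. State the class of each endpoint event (new systemic therapy, relapse, death and any other that can have a partial date).
2. Set the imputed date to the latest of the rule's date, the day after the last contact documenting the patient free of that event, the first dose date and, for DoR, the first response date. If the result falls outside the recorded month, query the record.
3. Cap month-end dates at the data cut-off.
4. Use the same imputed start of new therapy wherever that date is needed, including the response rule in SAP 5.1.1 and the corticosteroid analyses in SAP 8.4.2, and say that it overrides the concomitant-treatment rule.

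The cost is a few sentences and a maximum and minimum in the date derivation. No new data are needed, and dates already consistent with these bounds do not change.
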